1.0 Background

Heart failure patients with reduced left ventricular systolic function and worsening clinical status are frequently treated with mechanical devices. Cardiac resynchronization therapy (CRT) and left ventricular assist devices (LVAD) are mainstays of advanced heart failure treatment and have independently been demonstrated to decrease mortality. However, minimal research documents the utility of these two modalities in unison. There have been recent investigations comparing Biventricular (BiV) versus right ventricular (RV) pacing suggesting better exercise performance and decreased left ventricular (LV) volumes with RV pacing [1]. This discovery contrasts with prior meta-analysis that reports no difference between LVAD patients with and without CRT including mortality and hospitalizations [2]. We aim to compare BiV pacing and RV pacing in LVAD patients with CRT on patient's exercise tolerance and frequency of tachyarrhythmias. Additionally, research is required to form a conclusion on the role of CRT in LVAD patients.

2.0 Rationale and Specific Aims

The study is a randomized single-blind crossover prospective study in which we will determine the clinical outcomes of CRT pacing modalities in LVAD patients. Only patients are blinded. This is a small-scale study from which future larger scale randomized controls can be performed. The primary endpoint will be the effect of BiV and RV pacing setting on the 6-minute walk test. Secondary outcomes include:

1. To assess effect of BiV and RV pacing settings on serum NT-Pro-BNP (N-terminal pro-brain natriuretic peptide)
2. To assess effect of BiV and RV pacing settings on quality-of-life as measured by the EQ-5D-3L Quality of life questionnaire.

Tertiary endpoints for the study are listed below.

1. To assess effect of BiV and RV pacing settings on QRS width.
2. To assess effect of BiV and RV pacing settings on frequency of tachyarrhythmias.

3.0 Inclusion/Exclusion Criteria

Patients will be included if they meet the following parameters:

1. Patients with both an LVAD and CRT device with functional leads.
2. Age 18 years and older.
3. Ability to walk.
4. Ability to sign consent

Patients will be excluded if they meet the following parameters:

1. Patients with permanent Atrial Fibrillation
2. Patients who are pacemaker dependent
3. Patients with sustained ventricular tachycardia

4.0 Enrollment

We plan to have an open enrollment that will last for four months in order to discuss the study with all advanced heart failure patients at their routine quarterly appointment. There are approximately 60 patients we expect to meet criteria from IU Health Methodist Hospital, and we predict a minimum of 28 patients will participate. Informed consent will be obtained from patients using Appendix A (Informed Consent Statement). Patients will act as their own control in this crossover study spending three months in each of the different pacing modalities. Patients will be randomly placed into BiV or RV pacing setting upon enrollment. We will use a randomized cross-over design to assign patients as discussed below in statistical considerations. We will use Heart Failure Clinic routine follow-up visits which occur every three months as crossover points between the different pacing methods. All patients will be blinded to their pacing settings. The assessors will not be blinded to the pacing settings.

5.0 Study Procedures

Upon enrollment, we will collect patient characteristic at including 6-minute walk test, EKG, quality of life questionnaire, and NT-pro-BNP lab draw. In addition to this the CRT device will be interrogated and reprogrammed to a randomly assigned to BiV or RV pacing modality. They will be scheduled for a clinic visit in 3 months. During their return visit, they will undergo a 6-minute walk test, EKG, quality of life questionnaire (EQ-5D-3L Quality of life questionnaire), NT-pro-BNP lab draw, and device interrogation evaluating atrial arrhythmias and ventricular arrhythmias burden. Following completion of these tasks their CRT device will then be reprogrammed to the remaining pacing modality. This process will be repeated at 6-month appointment to complete a total of 3 months in each pacing modality.

The 6-minute walk test has been demonstrated to be an indicator of postoperative mortality in LVAD patients [3]. NT-pro-BNP can be a prognostic predictor of mortality in advanced heart failure. Device interrogation will be performed to evaluate lead impedance, determine quantity of tachyarrhythmias during testing period, and reprogram to next desired pacing modality.

6.0 Reporting of Adverse Events or Unanticipated Problems involving Risk to Participants or Others

Prior research has shown no difference between LVAD patients with and without CRT regarding mortality and hospitalizations [2]. There is no known significant risk above the inherent baseline risks of having a left ventricular device. Generally, CRT settings are maintained on BiV pacing though the pacing modality can be changed or turned off by the provider. However, recent research suggests that RV pacing may be beneficial to patients with improved functional status and quality of life [1]. While the exact mechanism for this benefit is unclear, we hope to mirror this result with BiV and RV pacing. The LVAD is controlling hemodynamic function and is not being altered for purposes of this study. There is no clear

indication that pacing modalities affects tachyarrhythmia rates; however, the information is easily gathered during device interrogation and will provide additional safety checks during the study. There is a theoretical risk of decreased functional status, which will be minimized with as each patient will spend only a brief 3 months in each modality and patient will be assessed at 3 months interval by their cardiologist. Advance heart failure patients with LVADs have routine 3-month appointments with laboratory tests with their primary cardiologist. All clinic visits and laboratory tests will be as clinically indicated and not explicitly for research purposes. Adverse events will be monitored throughout the study. Adverse events that meet IU HRPP Reportable Events criteria will be promptly reported to the IU IRB with 5 business days.

7.0 Statistical Considerations

Our primary endpoint is differences in 6-minute walk test between two pacing approaches. A sample size of a total n=24 subjects will allow us to detect an effect size 0.6 in a comparison of the two pacing methods with statistical power of 80% at the two-sided significance level of 0.05. We will randomize enrolled patients to either BiV or RV, and once they complete the 3 months of one modality, they will be switched to the other modality. To account for a patient attrition rate of 15%, we will randomize at least 28 patients.

For all subjects, we will assign study ids 1 to 28 to them in a sequential order based on time of enrollment (1 first, 28 last), such that each patient will undergo the pacing methods as ordered in the table below, where A stands BiV and B for RV. If more than 28 participants enroll, they will be assigned ids using consecutive integers from 29 and the statistician will create additional randomization assignments. The sequence (in terms of the order of pacing methods) will be as follows:

Pacing sequence AB: patients 2 6 7 8 11 13 15 16 17 20 22 24 25 27
Pacing sequence BA: patients 1 3 4 5 9 10 12 14 18 19 21 23 26 28

If patients elects to drop-out they will have the option to return to pre-study BiV pacing or to proceed to the next planned pacing assignment.

Analytical Plan: Briefly, descriptive data will be presented as mean \pm standard deviation (SD) and median and IQR as appropriate for continuous variables, or frequency and percentages for categorical variables. Statistical significance is set at 5% and nominal p-values are reported without multiple comparison adjustment. Regression analyses using linear mixed models or generalized estimating equations as appropriate for the outcome variable of interest will be used to assess the differences in pacing methods on each outcome variable while accounting for repeated measure correlations within each patient. Models will include subject (as a random effect), pacing method, period, sequence and residual treatment effect (carryover effects). The least square means as well as their confidence intervals for pacing method will be produced with and without carryover effects. Missing data are naturally handled by mixed effect models when data are missing at random. If GEE is used, multiple imputations will be employed before analysis.

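### Does randomizing 28 patients fall short of the stated 15% attrition allowance?

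*Combined protocol and SAP*

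**What the plan says.** Section 7.0 (Statistical Considerations) gives the sample size in two steps. First the evaluable number: "A sample size of a total n=24 subjects will allow us to detect an effect size 0.6", with 80% power "at the two-sided significance level of 0.05". Then the allowance for loss: "To account for a patient attrition rate of 15%, we will randomize at least 28 patients". The section lists the pacing sequence for ids 1 to 28, 14 in each order, and says what happens beyond that: "If more than 28 participants enroll, they will be assigned ids using consecutive integers from 29", with the statistician producing the extra assignments. Section 4.0 (Enrollment) expects about 60 patients to meet the criteria and predicts that no fewer than 28 will take part.

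The documents do not show the formula that led from 24 to 28. They also do not say in which standard deviation the 0.6 is expressed, and they give no difference or standard deviation in metres for the 6-minute walk test.

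**The concern.** The standard inflation for attrition divides the required number by the retained fraction and rounds up, because the requirement is a floor. Here that gives 29, not 28. A reader may suspect the common slip of multiplying by 1.15 instead: 24 × 1.15 = 27.6, which rounds up to 28. The base number has almost no slack, since 24 is the smallest number that reaches 80%. If the allowance is short, a trial that stops at 28 and loses 15% could fall below its stated power.

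A second doubt sits beside this one. If the 0.6 were in between-patient standard deviations, the power at 24 patients would depend on the correlation between a patient's two walk tests, which the documents do not give.

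**Working it through.** **Inputs, all from section 7.0:** 24 evaluable patients; effect size 0.6; two-sided 0.05; target power 80%; attrition 15%; at least 28 randomized.

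**1. The base number.** Take 0.6 as the mean within-patient difference divided by the standard deviation of those differences. Power then comes from the noncentral t distribution with noncentrality 0.6 × √n. The two columns use n − 1 degrees of freedom (paired t-test) and n − 2 (period also fitted).

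| Completers | Power, n − 1 df | Power, n − 2 df |
|---|---|---|
| 23 | 78.5% | 78.3% |
| 24 | 80.4% | 80.2% |

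The plan's 24 is reproduced.

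**2. The attrition step.**
- 24 / (1 − 0.15) = 28.24: 28 to the nearest integer, 29 rounded up.
- 24 × 1.15 = 27.6: 28 rounded up.
- 28 × 0.85 = 23.8 expected completers, which is 24 − 23.8 = 0.2 of a patient short.
- 29 × 0.85 = 24.65 expected completers.

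Two routes lead to 28, so the number alone does not show that the wrong formula was used. A preference for an even total, to split 14 and 14, would lead there too.

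**3. Whole patients.** 15% of 28 is 4.2. Four losses are 4/28 = 14.3% and leave 24. Five losses are 5/28 = 17.9% and leave 23. No whole number of losses at or below 15% takes 28 patients under 24.

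**4. Power at the expected number of completers.**

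| Randomized | Expected completers | Power, n − 1 df | Power, n − 2 df |
|---|---|---|---|
| 28 | 23.8 | 80.0% | 79.8% |
| 29 | 24.65 | 81.5% | 81.3% |

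**5. Chance variation in attrition.** Suppose each patient is lost independently with probability 0.15. Averaging the power over the binomial number of completers gives:

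| Randomized | P(at least 24 completers) | Average power, n − 1 df | Average power, n − 2 df |
|---|---|---|---|
| 28 | 59% | 79.8% | 79.6% |
| 29 | 74% | 81.2% | 81.1% |

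All the averages for 28 round to 80%.

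**6. The denominator of the effect size.** If 0.6 were in between-patient standard deviations with correlation ρ between the two periods, the paired effect size would be 0.6 / √(2(1 − ρ)). The values of ρ below are assumptions, as the documents give none. Power is for 24 patients with n − 1 df.

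| ρ | Paired effect size | Power |
|---|---|---|
| 0.3 | 0.507 | 66% |
| 0.5 | 0.600 | 80.4% |
| 0.6 | 0.671 | 88% |

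At ρ = 0.5 the two definitions coincide.

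**The case for a change.** The strongest case for a change is that a sample size is a floor, so 28.24 should become 29. The base number leaves only 0.2 to 0.4 of a percentage point above 80%. The prepared list stops at 28, so a trial that ends there complies with the plan and covers 14.3%, not 15%. With 28 randomized, the chance of keeping 24 completers is only 59%. The repair is one sentence.

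The arithmetic in this stands, and strict rounding does give 29. The consequences do not follow. The 59% describes chance variation around an expected-value inflation, which never promises that the target will be reached; at 29 it is still only 74%. The count of completers also somewhat overstates the loss, because section 7.0 plans mixed models that use incomplete data when these are missing at random, and multiple imputation if GEE is used. Enrolling a 29th patient is already within the plan.

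On the effect size, it is true that the denominator is not stated and that the range from 66% to 88% is far wider than anything one patient can cause. But that range comes from correlations supplied from outside the plan. Sections 4.0 and 7.0 describe a crossover in which each patient is their own control, and the paired reading returns the plan's own 24 at 80%. A statistician would read it that way without being told. A phrase saying so would be a courtesy to the reader.

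**Conclusion.** The concern does not call for a change. Strictly rounded up, 15% attrition with 24 completers needs 29 patients, and 28 covers up to 4 losses, or 14.3%. The gap is 0.2 of an expected patient, and power at the expected number of completers is 79.8% to 80.0%, which is the stated 80% to the precision given. Because 28 is a minimum with a provision for more, writing 29, or calling the allowance about 14%, would alter neither the design, nor the analysis, nor any conclusion. The missing denominator of the effect size is a reporting gap that the crossover design fills in the ordinary way.

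This rests on reading 0.6 as standard deviations of the within-patient difference, and on the comparison of pacing methods without a carryover term. The step-5 figures further assume that losses are independent at 15%.

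### Section 7.0 prints the pacing sequence for IDs 1 to 28, issues IDs by enrolment order and describes no concealment, so the next sequence can be known before consent and the baseline walk

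*Combined protocol and SAP*

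**What the plan says.** All references are to the combined protocol and SAP.

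- **Numbering (7.0 Statistical Considerations):** "we will assign study ids 1 to 28 to them in a sequential order based on time of enrollment (1 first, 28 last". The ID fixes the order of pacing, with A for BiV and B for RV.
- **The list (7.0):** "Pacing sequence AB: patients 2 6 7 8 11 13 15 16 17 20 22 24 25 27" and "Pacing sequence BA: patients 1 3 4 5 9 10 12 14 18 19 21 23 26 28".
- **Beyond 28 (7.0):** IDs continue from 29 and "the statistician will create additional randomization assignments". Nothing says that these will be withheld.
- **Timing (4.0 and 5.0):** "Patients will be randomly placed into BiV or RV pacing setting upon enrollment". Section 5.0 places the baseline 6-minute walk, EKG, questionnaire and NT-proBNP sample at enrolment as well, alongside the first reprogramming.
- **Blinding (2.0 and 4.0):** patients only; assessors know the setting.
- **Analysis (7.0):** "Models will include subject (as a random effect), pacing method, period, sequence and residual treatment effect (carryover effects", and "The least square means as well as their confidence intervals for pacing method will be produced with and without carryover effects".

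The documents mention no central or web release, no envelopes, no restriction on who holds the list, and no rule that the assignment follows consent and baseline testing. Section 8.0 names REDCap only for data storage.

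**The concern.** Concealment is about what staff know before a patient is assigned. It is a separate matter from the open assessment after assignment, which the protocol discloses, and it can be achieved even when assessors are unblinded. Here a reader of the protocol who knows how many patients have enrolled knows the next sequence. That knowledge could affect who is approached or consented at that moment, and how the effort-dependent baseline walk is conducted.

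In a crossover most of this cancels, because each completer is walked under both settings. What does not cancel is any comparison between the two sequence groups: the sequence/carryover comparison and, in some versions of the model, the pacing means with carryover fitted. Steering on expected change between periods would also reach the contrast without carryover, but that is harder to do, and nothing in the documents suggests that staff could predict such change.

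**Working it through.** **1. The list.** There are 14 AB and 14 BA entries, and IDs 1 to 28 each appear once. In ID order it reads B A B B B A A A B B A B A B A A A B B A B A B A A B A B. There is no constant block of 2, 4, 7 or 14. The predictability comes from printing the list and numbering by enrolment, not from small blocks.

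**2. Foreseeable assignments, out of 28.**

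| Information available | Expected correct | Certain |
|---|---|---|
| Printed list | 28 | 28 |
| Concealed 14:14 list, past assignments tracked | 16.8 | 2 × 14/15 = 1.9 |
| Concealed blocks of 4/6/8, past assignments tracked (simulation) | 18.9 | 0.6 |
| Pure chance | 14 | – |

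**3. The plan's sample size.** Section 7.0 gives n = 24, effect size 0.6, 80% power and two-sided 0.05. The plan does not define the effect size. Taking it as the mean difference over the SD of within-patient differences, power is 0.804 (23 df) or 0.802 (22 df), so the figure reproduces. I use n = 24 (12 per sequence) and 22 df below.

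**4. Two post-baseline periods.** Let g be a gap in level between the sequence groups (AB minus BA), π the period effect, and the true pacing effect zero. Expected cell means are AB: g, g + π; BA: 0, π.

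- Sequence fitted, no carryover: BiV − RV = ½[(AB₁ − AB₂) − (BA₁ − BA₂)] = ½[−π + π] = 0.
- All listed terms fitted: five fixed parameters on four cell means, rank 4 of 5, so one term must go.
- Carryover kept, sequence dropped: BiV − RV = AB₁ − BA₁ = g. The whole gap enters.

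Expected estimates on the printed list, with g = 0.1, 0.25 and 0.5 SD, correlations 0.5 to 0.8, and no dropout or four patients lost after period 1, give the same results.

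**5. Baseline as a third measure.** The plan does not say whether baseline enters the model. The drop-out provision, "return to pre-study BiV pacing", indicates that baseline would be under BiV. The full model then has rank 6 of 6 and the with-carryover estimate is (AB₁ − BA₁) − (AB₀ − BA₀).

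- Level gap: g − g = 0.
- Gap in the baseline walk only: 0 − g = −g. It enters in full.
- Sequence kept, no carryover, baseline-only gap: 0 with no dropout, at most 0.046 of the gap with the dropout patterns above.
- Carryover kept, sequence dropped, level gap: 0.2 to 0.5 of the gap.

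**6. Sequence/carryover test.** Noncentrality = g/√((1 + ρ)/2) × √6, where ρ is the correlation between periods.

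| g (SD) | ρ = 0.5 | ρ = 0.8 |
|---|---|---|
| 0.1 | 0.283, rejects 5.8% | 0.258, rejects 5.7% |
| 0.25 | 0.707, rejects 10.4% | 0.645, rejects 9.5% |

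**7. Steering on expected change (no-carryover contrast).** Suppose a share f of enrolments is perfectly sorted on a predictor correlated r with between-period change. The gap is 2 × 0.798 × f × r = 1.596fr, in SD of the within-patient difference, and the bias is half of it. The documents give neither f nor r; both are assumptions.

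- f = r = 0.1: gap 0.016, bias 0.008, noncentrality 0.008 × √24 = 0.04, rejection 5.0%.
- f = r = 0.3: gap 0.144, bias 0.072, noncentrality 0.072 × √24 = 0.35, rejection 6.3%.

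**8. Room to steer.** Section 4.0 plans to approach all patients at quarterly visits over four months. If visit timing is uniform, a second visit falls in the window only when the first is in month 1: probability 1/3, or 20 of about 60. A minimum of 28 of about 60 is predicted to join, so some choice remains.

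**The case against.** The strongest reply is that the primary result is barely touched. The endpoint is a within-patient difference. With sequence fitted and no carryover, a level gap does nothing, and even assumed steering on expected change moves the false-positive rate only to 6.3%. That stands, and it limits how serious this is.

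A second reply is that the exposed outputs depend on analysis choices. With two periods, sequence and carryover cannot both be fitted, and that defect exists however well allocation is concealed. The use of baseline as a repeated measure is a possible reading, not something the plan states; Section 5.0 treats the enrolment data as patient characteristics. Both points are fair. But Section 7.0 commits to pacing means with carryover and does not say which model produces them, so these routes cannot be ruled out.

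A third reply is that the useful comparison is 28 against about 16.8, not against 14, because unblinded staff can track past assignments. I accept that; the difference is still large. Foreknowledge also requires the current enrolment count, and the documents do not record who held the list.

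Finally, if enrolment has closed, only disclosure and a baseline table by sequence remain possible. That is correct, and the fix covers it.

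**Conclusion.** The concern holds. Followed as written, the plan makes all 28 listed assignments foreseeable before consent and before the baseline walk. That rests on the text alone and is certain. The documents do not show that the knowledge was used.

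The consequences rest on assumed gap sizes. For the pacing contrast with sequence fitted and no carryover, bias is zero under a level gap and 0.01 to 0.07 SD under the assumed steering. The sequence/carryover test rejects falsely about 6% or 10% of the time at gaps of 0.1 or 0.25 SD. The with-carryover pacing means take the full level gap only if two periods are modelled and sequence is dropped. They take a full baseline-only gap if baseline is a repeated measure and sequence is kept. The plan should be changed because the protection is cheap, not because bias in the primary result has been shown.

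**What to change.** - Remove the list from the protocol. For patients not yet randomised, replace it with a new list generated by the statistician and withheld from recruiting and assessing staff.
- Release each assignment only after consent, the baseline 6-minute walk, EQ-5D-3L and NT-proBNP sample are recorded. Use REDCap if its randomisation function is available, otherwise sealed sequential envelopes.
- Apply the same rule to IDs 29 onward.
- For patients already randomised, state who had access to the list and report the baseline walk by sequence.

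Randomly varied blocks of undisclosed size are preferable if the list is replaced part-way or enrolment may stop away from 28: stopping at 24, the mean imbalance is about 0.6 patients with blocks of 4/6/8 and 1.4 with a single list. The price is more correct guesses from past assignments (18.9 against 16.8 of 28), though fewer certain ones (0.6 against 1.9). A concealed 14:14 list would also do; the statistician can weigh the two.

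The cost is a short amendment and some set-up work, with no extra patients or visits. Because the protocol documents REDCap for storage only, its randomisation function must be checked first.

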8.0 Privacy/Confidentiality Issues

No personal information will be published. Primary data will be collected via patient interview and stored electronically in REDCap. The storage location will be backed up automatically every day. Other data sources include lab data and device interrogations are automatically stored in patient's electronic medical records and will be merged with the primary data as needed. Quality assurance steps will include: testing of database by study team prior to moving to production mode. The following quality control methods will be used: single entry with random checks of accuracy and 2) extraction and cleaning of data that will be used for analysis every 6 months. Once patient data is initially collected, it will be de-identified before analysis.

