9.0 Follow-up and Record Retention

Patients will spend approximately 3 months in each of the pacing settings. Follow up will be scheduled to match their routine outpatient clinic follow appointments which occur every three months. At their routine clinical follow-up appointments, we will collect data at the 3- and 6-month marks following enrollment. At these visits, they will undergo 6-minute walk tests, device interrogation, NT-pro-BNP lab draw (N-terminal (NT)-pro hormone B-type natriuretic peptide), EKG, and quality of life screening questionnaire. Then the pacemaker device will be reprogrammed to the next pacing modality. Data will be kept in an encrypted Excel worksheet until the data is analyzed for publications.

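### Does the plan need a written rule for walk tests obtained after a patient drops out and changes pacing mode?

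*Combined protocol and SAP*

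**What the plan says.** All in the combined protocol and SAP.

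- **Section 7.0, switching.** The planned course is that "once they complete the 3 months of one modality, they will be switched to the other modality". Patients who drop out are treated separately: "they will have the option to return to pre-study BiV pacing or to proceed to the next planned pacing assignment".
- **Section 7.0, sample size.** 24 subjects give 80% power for effect size 0.6 at two-sided 0.05, and "To account for a patient attrition rate of 15%, we will randomize at least 28 patients".
- **Section 7.0, Analytical Plan.** "Models will include subject (as a random effect), pacing method, period, sequence and residual treatment effect (carryover effects"). For absent values: "Missing data are naturally handled by mixed effect models when data are missing at random". Multiple imputation is kept for GEE.
- **Sections 4.0, 5.0 and 9.0, visits.** The routine three-monthly visits are the crossover points. The device is reprogrammed after that visit's tests are done. Section 9.0 adds that "we will collect data at the 3- and 6-month marks following enrollment".
- **Sections 6.0 and 8.0, routine records.** "Advance heart failure patients with LVADs have routine 3-month appointments with laboratory tests with their primary cardiologist". Laboratory and interrogation data sit in the medical record and "will be merged with the primary data as needed".

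No section names an analysis set, says whether values after drop-out are used, or defines the pacing term as planned or delivered mode.

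**The concern.** A patient who drops out may be paced in a mode other than the one scheduled for that period. If that patient is still walk-tested at month 3 or 6, both walks may come from the same mode. There are then three possible analyses: by planned mode, by delivered mode, or with the off-plan value set to missing. By planned mode, such a patient contributes an expected difference of zero and pulls the estimate towards no effect, even if drop-out is random.

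The collection times run from enrollment, not from the switch, so a patient who moved on early could be in the second mode at the month-3 mark. Section 4.0 says assessors know the pacing setting, so a rule settled late might not be settled blind. With 28 patients and one primary comparison, a few such values could matter.

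**Working it through.** **1. The plan's own figure.** Inputs from section 7.0: n = 24, effect 0.6, two-sided 0.05. Assumption: the effect is in units of the SD of the within-patient difference, which the plan does not define. The noncentrality is 0.6 × √24 = 2.94. Paired t power is 0.804 on 23 df (0.802 on 22 df with period fitted), so the stated 80% reproduces. For attrition, 28 × 0.85 = 23.8, or about 24 pairs. The sample size therefore treats drop-outs as giving no usable pair.

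**2. When a value can be off plan** (A = BiV, B = RV).

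| Drop-out in | Planned mode | Returns to BiV | Proceeds | Off-plan value possible? |
|---|---|---|---|---|
| AB, period 1 | BiV | BiV, also at month 6 (RV planned) | RV, early | Yes |
| AB, period 2 | RV | BiV | nothing left | Yes |
| BA, period 1 | RV | BiV | BiV | Yes, if switched before the visit |
| BA, period 2 | BiV | BiV | nothing left | No |

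The fourth row cannot go off plan. If drop-outs spread evenly over the four rows, at most three quarters are affected. The 15% allowance is about four patients, and 4 × 3/4 = 3. Even that requires every one of them to return for a study walk test, which no section provides for. A patient who proceeds at a scheduled visit is measured before reprogramming, so that month-3 value is on plan. A switch between visits is not excluded, but it is an assumption.

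**3. Size if off-plan walks were analysed under the planned label.** With k such patients among 28:

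- expected estimate = 0.60 × (28 − k)/28
- SD of the mixed differences = √(1 + 0.36 × (k/28) × (1 − k/28))
- if those values are set to missing, 28 − k pairs remain and the estimate is 0.60

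For k = 3 the estimate is 0.60 × 25/28 = 0.536 and the SD is 1.017, so the noncentrality is (0.536/1.017) × √28 = 2.79 and power is 0.766. With the values missing, it is 0.6 × √25 = 3.00 and power is 0.821.

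| k | Estimate, planned label | Power, planned label | Power, set missing (estimate 0.60) |
|---|---|---|---|
| 0 | 0.600 | 0.864 | 0.864 |
| 1 | 0.579 | 0.835 | 0.851 |
| 2 | 0.557 | 0.802 | 0.836 |
| 3 | 0.536 | 0.766 | 0.821 |
| 4 | 0.514 | 0.728 | 0.804 |

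The k = 4 row exceeds what four evenly spread drop-outs can give and is shown only as a bound.

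**4. Check by simulation.** A mixed model with random subject, pacing, period and sequence was fitted to the plan's own allocation list. Assumptions: within-patient correlation 0.7, random drop-out, 6,000 runs per case. At k = 3 and true effect 0.60 the mean estimates were 0.534 (planned), 0.597 (delivered) and 0.597 (missing), with power 76.3%, 82.3% and 82.2%. Delivered-mode and set-missing estimates agreed to three decimals in every case, so the real contrast is planned label against the other two. The three rules disagreed on p < 0.05 in 5.2%, 8.5% and 11.2% of trials for k = 1, 2 and 3. With no true effect, each single rule stayed near 5%. Picking the most favourable of the three gave 6.0%, 6.6% and 7.0%.

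**5. If no value after drop-out is used,** none of this arises and step 1 stands.

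**The case for a change.** The best argument for a change is that nothing in the text strictly settles the matter. The attrition allowance is a sample-size input, not an analysis rule. The missing-at-random sentence concerns absent values, not values observed in another mode. An option to move on to the next assignment can be read as staying in the trial, and the visit schedule does not set drop-outs apart. A written rule would cost a few sentences, and assessors are unblinded.

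The silence is real, and the dilution arithmetic is correct. Stray off-plan values are also plausible for NT-pro-BNP and device interrogation, because those come from routine records. But these are secondary and tertiary outcomes, reported with nominal p-values. The routine-care text mentions laboratory tests and interrogations and does not extend to the 6-minute walk. The false-positive figures require someone to try all three rules and keep the best; unblinded assessors do not show that whoever chooses the rule would do so. Nor is there a stated rule that gives a wrong answer. The rule one would write, setting off-plan values to missing, is the one the 24-of-28 calculation already implies.

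**Conclusion.** No change to the plan follows. This is a gap that an analyst would fill sensibly: drop-outs are budgeted as lost, their later values are missing, and the mixed model uses what was obtained as planned. On that reading the effect on the primary result is nil.

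The reading rests on the attrition allowance and on the order of procedures at visits, not on an explicit sentence. If it were wrong, the loss would still be limited: 0.58 against 0.60 with one off-plan walk, and about 0.54 against 0.60 with power near 77% against 82% with three. Those figures assume random drop-out, an effect in units of the within-patient difference SD, and walk tests that the documents do not schedule. If drop-out were related to response, setting values to missing could itself be biased, and choosing between planned and delivered labels would not cure that. For a study that section 2.0 describes as small and meant to inform larger trials, the point does not warrant a revision.
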